**Effects of High-Intensity Interval Training and Strength Training
On Levels of Testosterone and Physical Activity among Women with
Polycystic Ovary Syndrome.**

ClinicalTrials registration no: NCT04942366

Date: 9-March-2021

Statistical Analytical Plan:

For the analysis, the data was entered and analyzed in MedCalc software version 19.0.5.

Descriptive statistics were performed for demographic information and this data is presented in terms of frequency and percentage. Shapiro-Wilk test was used to determine the normality of data.

For BMI: Shapiro-Wilk test was used to determine the normality of data and the data was normally distributed so paired T-test was performed for within group analysis. Independent T-test was performed for the comparison between the two groups.

For Serum testosterone: Shapiro-Wilk test was used to determine the normality of data and the data was normally distributed so paired T-test was performed for within group analysis. Independent T-test was performed for the comparison between the two groups.

For Body fat percentage: Shapiro-Wilk test was used to determine the normality of data. The data was not normally distributed so, Wilcoxon sign rank test was performed for within group analysis. Independent T-test was performed for the comparison between the two groups.

For IPAQ: Shapiro-Wilk test was used to determine the normality of data. The data was not normally distributed so, Wilcoxon sign rank test was performed for within group analysis. Independent T-test was performed for the comparison between the two groups.

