**Effects of High-Intensity Interval Training and Strength Training
On Levels of Testosterone and Physical Activity among Women
with Polycystic Ovary Syndrome.**

ClinicalTrials registration no: NCT04942366

Date: 9-March-2021

Study Protocol:

Informed consent had been taken from the participants before inclusion in the study. Baseline assessment was done before the start of the session. Both groups performed the warm up and cool down session. Group A performed High intensity interval training and Group B performed strength training exercises. The total length of this planned study was 36 sessions in 12 weeks i.e. three sessions per week. For baseline assessment, Laboratory test for total serum testosterone was performed, skinfold measurement for body fat had been taken by the chief examiner and International physical activity questionnaire for physical activity measurement was filled by the subjects. At the end of the last intervention session, all outcome measures were reassessed (post- intervention). All the activities were supervised by a physical therapist.

Warm Up:

A total of 10 minute warm up of light to moderate intensity cardiorespiratory activity for HIIT group A and muscular endurance activity for ST group B.

High Intensity Interval Training:

High intensity interval training for group A was performed thrice a week using a treadmill. The protocol of each session that was followed is four sets of 4 minute interval session (at 90%-95% of the individual HR max calculated by using the karvonen method) and each set had been followed by 3 minute of moderate intensity exercise (at 70% of individual HR max, calculated through karvonen method). Each session was of 45 minutes duration including warm up and cool down period. To ensure that the correct exercise intensity is

performed; subjects wore heart rate monitors during training sessions.

Strength Training:

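### With both arms training, the SAP's eight within-arm tests cannot show a training effect; conclusions should rest on a baseline-adjusted comparison between arms

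*SAP*

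**What the plan says.** The Protocol describes two active arms: "Group A performed High intensity interval training and Group B performed strength training exercises". Sessions run three times a week for 12 weeks in both arms, and no untrained arm is described. On measurement it says: "For baseline assessment, Laboratory test for total serum testosterone was performed, skinfold measurement for body fat had been taken by the chief examiner", with the physical activity questionnaire also completed at baseline. At follow-up, "At the end of the last intervention session, all outcome measures were reassessed".

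The SAP treats four outcomes in turn. For BMI and serum testosterone, "the data was normally distributed so paired T-test was performed for within group analysis". For body fat percentage and IPAQ, "The data was not normally distributed so, Wilcoxon sign rank test was performed for within group analysis". Under all four outcomes the same sentence follows: "Independent T-test was performed for the comparison between the two groups".

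The SAP does not say whether the independent t-test is applied to post values or to changes, and mentions no adjustment for baseline. Neither document names a primary analysis or says which kind of test supports a conclusion.

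**The concern.** A before-after test in a single trained arm asks whether the mean or typical value moved. It does not ask why. Regression to the mean, time, and anything else that changed over 12 weeks enter the result together with training, and no untrained arm is available to subtract them.

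Two misreadings follow. A significant within-arm change may be reported as an effect of that programme. A split result, with one arm significant and the other not, may be reported as one programme working better, although comparing two p-values is not a test of the difference between arms. The shared title, "Effects of High-Intensity Interval Training and Strength Training", can be read as promising a statement about each programme, which makes the first misreading easier; it can equally be read as comparative.

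Separately, if the between-arm t-test ignores baseline values that are already in hand, precision is given away.

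**Working it through.** **Count of tests (from the SAP).** Within-arm: 4 outcomes × 2 arms = 8 (4 paired t, 4 Wilcoxon), taking the within-group analysis as run once in each arm. Between-arm: 4 outcomes × 1 = 4.

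**Inputs.** The documents give no sample size, alpha, SD or pre-post correlation, so there is no stated figure to reproduce. Everything below is assumed: two-sided 0.05; 15, 20 or 30 per arm; correlation ρ of 0.5–0.7; normal data; equal SD before and after.

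**Step 1: within-arm tests when training does nothing (illustration only).** Let both arms drift by the same amount δ, in SD units.
- Standardised paired effect: d = δ / √(2(1 − ρ)).
- The probability p of significance comes from the non-central t with n − 1 degrees of freedom and non-centrality d√n.
- The arms contain different people, so the probability that exactly one arm is significant is 2p(1 − p).

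For δ = 0.3:
- ρ = 0.5, n = 15: d = 0.3/√1 = 0.300, p = 0.19, exactly one arm 2 × 0.1915 × 0.8085 = 0.31.
- ρ = 0.7, n = 30: d = 0.3/√0.6 = 0.387, p = 0.54, exactly one arm 2 × 0.5362 × 0.4638 = 0.50.

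Over n = 15–30 and ρ = 0.5–0.7:

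| Shared drift (SD) | Paired t significant | Exactly one arm significant |
|---|---|---|
| 0.1 | 6.5–10.5% | 12–19% |
| 0.3 | 19–54% | 31–50% |
| 0.5 | 44–93% | 13–49% |

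No figure is given for the Wilcoxon tests, because the SAP calls those data non-normal and gives no distribution.

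**Step 2: between-arm test under the same drift.** A drift common to both arms cancels in the difference. In simulation (20,000 runs per cell, no true difference, ρ 0.5–0.7) the rejection rate was 4.7–5.3% on post values, 4.8–5.2% on change and 4.7–5.2% with ANCOVA. All three hold their error rate, so the case for ANCOVA is precision.

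**Step 3: precision.** Large-sample variances of the between-arm estimate are proportional to 1 (post values), 2(1 − ρ) (change) and 1 − ρ² (ANCOVA).
- ANCOVA against post: 0.75/1 at ρ = 0.5 and 0.51/1 at ρ = 0.7, so 25–49% lower variance.
- ANCOVA against change: 0.75/1 at ρ = 0.5 and 0.51/0.60 = 0.85 at ρ = 0.7, so 15–25% lower variance.

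Simulated mean 95% CI half-widths, in SD:

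| n per arm | ρ | Post | Change | ANCOVA | Narrower than post | Narrower than change |
|---|---|---|---|---|---|---|
| 15 | 0.5 | 0.741 | 0.741 | 0.654 | 12% | 12% |
| 15 | 0.7 | 0.741 | 0.573 | 0.539 | 27% | 6% |
| 30 | 0.5 | 0.515 | 0.514 | 0.449 | 13% | 13% |
| 30 | 0.7 | 0.514 | 0.398 | 0.371 | 28% | 7% |

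**Step 4: the two outcomes called non-normal.** With assumed lognormal data (log-SD 0.5 and 1.0) and no true difference, plain ANCOVA rejected 4.0–4.9% of the time and rank ANCOVA 4.7–5.5%. The ordinary ANCOVA interval covered about 95–96.5%; a percentile-bootstrap interval covered about 92–94%, and it disagreed with the rank-ANCOVA p-value on significance in about 5–8% of simulated trials. One method should therefore supply both interval and p-value.

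**The case against.** The SAP gives each test a role. The paired and Wilcoxon tests are labelled as within-group, and the question of whether the arms differ is sent to an independent t-test under every outcome. Nothing proposes inferring a difference from a split result. A reader might infer that the plan draws its conclusions from the before-after tests, or has no sound test between arms. The documents support neither reading: they state no conclusion, and under the assumptions above the t-test holds its 5% error rate on post values or on change. That part of the objection stands.

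It also stands that the drift figures have no anchor in the documents. Across the table the paired-t rate runs from 6.5% to 93%; this shows what is possible and says nothing about how much drift occurred here.

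A further fair point is that replacing within-arm p-values with confidence intervals changes little by itself. For the paired t-test, a 95% CI excludes zero exactly when p < 0.05, so the explicit caveat has to do the work.

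The objection does not remove the rest. Nothing in either document marks the within-arm results as descriptive or gives the between-arm comparison priority, and nothing says that the baseline values enter that comparison.

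**Conclusion.** The point holds as a risk of interpretation together with a better available method, and not as an error in the between-arm test. The within-arm tests cannot show a training effect in this design; that follows from the two trained arms and needs no assumed number.

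The measurable gain is in precision. A 95% CI about 12–28% narrower than with post values, or, if the t-test already uses change, a large-sample variance 15–25% lower, rests on assumed correlations of 0.5–0.7, 15–30 per arm for the CI figure, and normal data. The 19–54% rate for a paired test at 0.3 SD drift is illustration only.

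Two neighbouring matters are separate. How participants were allocated is not described in these documents, and a causal reading of the between-arm difference depends on it. Four between-arm tests without a named primary outcome also remain after this change.

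**What to change.** 1. Base conclusions on the between-arm comparison of post values adjusted for baseline (ANCOVA), one per outcome, reported as a difference with 95% CI. For body fat percentage and IPAQ, take the interval and the p-value from one method: for example the ordinary ANCOVA interval with its own p-value, and rank ANCOVA as a sensitivity analysis. Do not pair a bootstrap interval with a rank-ANCOVA p-value.
2. Present the eight within-arm changes as descriptive estimates, and state that without an untrained arm they are not evidence of a training effect. Dropping the p-values without that statement is not enough.
3. Label the ANCOVA post hoc. The SAP is written in the past tense, reports the outcome of the normality tests and says "For the analysis, the data was entered and analyzed in MedCalc software version 19.0.5", which indicates that the data had been seen.

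**Cost.** No new data: a revised analysis text, four ANCOVAs and eight descriptive summaries. The Protocol's baseline list omits BMI, but a paired t-test on BMI implies that a baseline value exists. The sponsor loses the within-arm significance claims and must accept the post hoc label.

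### Optional, nearly free improvement: the arms are compared by an unadjusted t-test on all four outcomes; a labelled post-hoc ANCOVA on baseline would often be more precise, by an amount the documents do not fix.

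*SAP*

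**What the plan says.** The SAP deals with BMI, serum testosterone, body fat percentage and IPAQ in turn, and each paragraph ends with the same sentence: "Independent T-test was performed for the comparison between the two groups". No covariate is named, and nothing says whether the test was applied to post-intervention values or to changes. Baseline enters the SAP only through the within-group tests: a paired t-test for BMI and testosterone, and a signed-rank test for body fat and IPAQ ("The data was not normally distributed so, Wilcoxon sign rank test was performed for within group analysis").

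The Protocol (Study Protocol) shows that the covariate is available for three outcomes: "For baseline assessment, Laboratory test for total serum testosterone was performed", and "skinfold measurement for body fat had been taken by the chief examiner and International physical activity questionnaire for physical activity measurement was filled". After training, "At the end of the last intervention session, all outcome measures were reassessed". BMI is not in the Protocol's list of baseline measurements. A baseline BMI is implied only by its paired test in the SAP: "For BMI: Shapiro-Wilk test was used to determine the normality of data and the data was normally distributed so paired T-test was performed".

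Two further facts limit what can be proposed. The Protocol names the arms ("Group A performed High intensity interval training and Group B performed strength training exercises") but does not describe how women were allocated to them. The SAP is written after the event ("the data was entered and analyzed in MedCalc software version 19.0.5") and already reports normality results, so any added model is post hoc.

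**The concern.** Each outcome has one baseline and one post-intervention value. A t-test on post values makes no use of baseline. A t-test on changes does use it, but fixes the slope of post on baseline at 1. ANCOVA estimates the slope, so in large samples its variance is no greater than that of either t-test. In small samples it pays a modest price for the estimate.

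The two t-tests also respond in opposite directions to a chance baseline gap. With equal SDs, a gap of D SD shifts the post-value comparison by rD and the change comparison by -(1-r)D. At r = 0.5 and D = 0.3 these are +0.15 and -0.15 SD. ANCOVA removes the shift on average under random allocation, though not exactly in any one trial.

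At stake is the precision of the comparison of interval training with strength training, obtained from data already collected.

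**Working it through.** **Inputs.** From the documents: two arms, one baseline and one post value per outcome, an independent t-test, no covariate. There is no stated sample size, SD, alpha, power or correlation, so there is no figure of the plan's own to reproduce. Assumed: equal arms, n = 15 per arm (10 and 30 as a range), two-sided 5%, linearity, normal errors, random allocation. Let r be the pre-post correlation and k the post SD divided by the pre SD.

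**Small-sample cost of ANCOVA.** Expected variance factor 1 + 1/(2n-4): 1 + 1/26 = 1.038 at n = 15; 1.0625 at n = 10; 1.018 at n = 30.

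**Against a post-value t-test.** Variance ratio (1-r²) × factor, whatever the value of k. At n = 15:
- r = 0.5: 0.75 × 1.038 = 0.779, 22% lower.
- r = 0.7: 0.51 × 1.038 = 0.530, 47% lower.
- Break-even r = √(1 - 1/1.038) = 0.19 (0.24 at n = 10, 0.13 at n = 30).

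**Against a change-score t-test, k = 1.** Variance ratio (1+r)/2 × factor. At n = 15:
- r = 0.5: 0.75 × 1.038 = 0.779, 22% lower.
- r = 0.7: 0.85 × 1.038 = 0.883, 12% lower.
- Break-even r = 2/1.038 - 1 = 0.93 (0.88 at n = 10, 0.96 at n = 30).

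**Against a change-score t-test, unequal SDs.** Variance ratio k²(1-r²)/(k²+1-2rk) × factor. At n = 15:

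| k | r | ratio before factor | after × 1.038 | ANCOVA variance |
|---|---|---|---|---|
| 1.3 | 0.5 | 1.2675/1.39 = 0.912 | 0.947 | about 5% lower |
| 1.3 | 0.7 | 0.8619/0.87 = 0.991 | 1.029 | about 3% higher |
| 1.3 | 0.8 | 0.6084/0.61 = 0.997 | 1.036 | about 4% higher |
| 0.8 | 0.5 | 0.48/0.84 = 0.571 | 0.593 | about 41% lower |
| 0.8 | 0.7 | 0.3264/0.52 = 0.628 | 0.652 | about 35% lower |

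The gain vanishes when the slope rk is close to 1. At k = 1.3, ANCOVA first stops gaining at r of about 0.6. The ratio before the factor never exceeds 1, so the expected loss cannot exceed about 4% in variance at n = 15.

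**Power.** Non-central t with 28 degrees of freedom for the t-test and 27 for ANCOVA, averaged over the chance baseline gap, with the true difference set so that the t-test has 80% power at n = 15:

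| Original test | ANCOVA power at r = 0.5 | at r = 0.7 | worst case |
|---|---|---|---|
| Post values | 89% | 97% | 78.4% (r = 0) |
| Changes, k = 1 | 89% | 85% | 78.6% at r = 0.99, tending to 78.4% as r approaches 1 |

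**Skewed outcomes.** The SAP calls body fat and IPAQ non-normal, so the power figures do not carry over to them directly. As a check of direction only, in simulated lognormal data with equal SDs (skewness 1.75, 15 per arm, 20,000 trials per setting), ANCOVA variance was 25% and 50% below post values, and 24% and 16% below changes, at r = 0.5 and 0.7.

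**If allocation was not random.** Take a true baseline gap of 0.3 SD, equal SDs and no treatment effect. If the gap would have persisted, ANCOVA is off by 0.3(1-r), which is 0.15 SD at r = 0.5 and 0.09 at r = 0.7, and the change score by 0. If it would have shrunk to r times its size, ANCOVA is off by 0 and the change score by -0.15 and -0.09 SD.

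**The case against.** The strongest reply is that nothing here is an error. Under random allocation a t-test on either scale holds its 5% type I error, and the ANCOVA proposed would not replace it. That stands, and is why the point is optional.

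Second, the size of the gain is assumed throughout. That also stands. A reader might take the 47% variance reduction, or the rise from 80% to 97% power, as the loss in this trial. The documents do not support that: it needs post values to have been tested and r to be 0.7, and neither is stated. If changes were tested, the gain depends on equal SDs as well as on r and can turn into a small loss at an ordinary correlation.

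Third, the change is not entirely free. Four between-group tests become ten (four t-tests, four ANCOVAs, two rank-based tests), after the data were seen, with no primary outcome named and no multiplicity control. A post-hoc label, a fixed set of analyses and a rule for disagreement reduce this problem but do not remove it.

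Two other inferences should be resisted. One is that the plan ignores baseline altogether: its within-group tests use it, and the between-group test may have been on changes. The other is that ANCOVA would correct an imbalance in how the arms were formed. Allocation is not described, and without randomisation ANCOVA and change scores can estimate different quantities.

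**Conclusion.** The point holds as an optional improvement. It is certain that the SAP names no baseline covariate for the between-group comparison of any of the four outcomes and does not say what the t-test compared. Given random allocation, the gain over a post-value test is robust once r exceeds about 0.2 at 15 per arm. The gain over a change-score test is conditional on r and on the ratio of post to pre SD, and is larger when the post SD is the smaller of the two. Confidence in the size is moderate at best, because sample size, SDs and r are all assumed. The possible loss is small: at most about 1.6 points of power at 15 per arm, from 80% to 78.4%.

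**What to change.** Add to the SAP, for example:

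> Post-hoc adjusted analysis, specified after the data were seen. For BMI, serum testosterone, body fat percentage and IPAQ score, the post-intervention value is analysed by ANCOVA on group, with the baseline value of the same outcome as covariate. The adjusted difference and its 95% CI are given for all four outcomes, whatever the result, beside the original independent t-test, which remains the reported comparison if the two disagree. For body fat percentage and IPAQ, a rank-based ANCOVA (Quade) is always given as well. No model or transformation is chosen from a residual check.

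Also state, for each outcome, whether the original t-test used post values or changes; confirm that baseline BMI was recorded; and state how women were allocated. If allocation was not random, show ANCOVA and change-score estimates side by side and do not claim that adjustment removes bias.

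Cost: SAP wording and a short re-analysis of existing data, with no new patients or measurements. Each model uses one degree of freedom and carries an expected variance penalty of about 4% at 15 per arm (6% at 10, 2% at 30), already counted in the figures above. The added tests are post hoc and without multiplicity control, and should be read as sensitivity analyses.

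### Neither document names a primary outcome, a significance level or a multiplicity rule, so the four between-group tests carry about a 9% to 19% chance of at least one false positive at an assumed 5% each

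*SAP*

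**What the plan says.** The SAP, under its Statistical Analytical Plan heading, gives four outcomes one parallel paragraph each:

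- BMI: "For BMI: Shapiro-Wilk test was used to determine the normality of data and the data was normally distributed so paired T-test was performed" within groups.
- Serum testosterone: "For Serum testosterone: Shapiro-Wilk test was used to determine the normality of data and the data was normally distributed so paired T-test was performed" within groups.
- Body fat percentage: "For Body fat percentage: Shapiro-Wilk test was used to determine the normality of data". Normality was not found, so "Wilcoxon sign rank test was performed for within group analysis".
- IPAQ: "For IPAQ: Shapiro-Wilk test was used to determine the normality of data", with the same result and the same within-group test as body fat.

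Every paragraph closes with the same between-group sentence: "Independent T-test was performed for the comparison between the two groups". It does not say whether the values compared are post-intervention values or changes from baseline.

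The Protocol describes two exercise groups: "Group A performed High intensity interval training and Group B performed strength training exercises". It has one assessment at baseline and one after the last session, and describes no untreated group.

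The title puts forward two of the four outcomes ("On Levels of Testosterone and Physical Activity among Women with" polycystic ovary syndrome). Neither document designates a primary outcome or primary comparison, states a significance level, gives a rule for success or adjusts for multiple testing.

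**The concern.** Four between-group tests with no stated order and no adjustment leave the error rate of the comparison uncontrolled, even if the plan is followed exactly. If one of the four reaches significance, nothing in the plan tells a reader whether it is the decisive result or one of several chances.

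The within-group tests raise a second difficulty. They are two-thirds of the planned tests, and the SAP does not say what they may be used for. With two active arms and no untreated control, a before-after change in either arm cannot be separated from the passage of time, regression to the mean or the effect of being measured again. A significant change in one arm and not in the other does not show that the arms differ.

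**Working it through.** **Inputs**

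- Outcomes: 4 (SAP).
- Arms: 2; assessments: baseline and post-intervention (Protocol).
- Significance level: not stated. Assumed two-sided 5% per test.
- Correlation between the test statistics of different outcomes: not stated. Taken as equal for all pairs and varied from 0 to 0.9.
- Sample size and effect size: not stated, and not needed for an error-rate calculation under the null.

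The plan gives no error rate, so there is no figure of its own to reproduce.

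**Step 1: number of tests.** Between groups: 4 × 1 = 4. Within groups: 4 × 2 = 8. Total: 12, not counting the normality checks.

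**Step 2: four between-group tests, independent.** The chance of at least one false positive is 1 − (1 − 0.05)^4 = 1 − 0.8145 = 0.1855, or 18.5%.

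**Step 3: four between-group tests, correlated.** With equal correlation ρ, each statistic is written as √ρ·U + √(1 − ρ)·E, where U is shared and both parts are standard normal. The chance of at least one false positive is one minus the average over U of

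[Φ((1.96 − √ρ·U)/√(1 − ρ)) − Φ((−1.96 − √ρ·U)/√(1 − ρ))]^4

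Numerical integration gives:

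| ρ | At least one false positive | Multiple of 5% |
|---|---|---|
| 0 | 18.5% | 3.7 |
| 0.3 | 17.4% | 3.5 |
| 0.5 | 15.6% | 3.1 |
| 0.7 | 13.0% | 2.6 |
| 0.9 | 9.4% | 1.9 |

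A separate simulation with 400,000 replicates agrees to within 0.1 percentage point.

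**Step 4: the two title outcomes only.** 1 − 0.95^2 = 0.0975, or 9.75%, if independent. The same integration with power 2 gives 8.3% at ρ = 0.7 and 7.0% at ρ = 0.9.

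**Step 5: after correction.** Bonferroni across the four uses 0.05/4 = 0.0125 per test, which gives 1 − (1 − 0.0125)^4 = 0.0491, or 4.9%, if independent. A single primary comparison fixed in advance carries 5%.

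**The case against.** The strongest reply is that the SAP makes no confirmatory claim. It states no significance level and no success criterion, so there is no error rate for it to breach. The title already gives prominence to testosterone and physical activity, and both documents cite a registration whose contents cannot be seen here and might name a primary outcome. BMI and body fat percentage are probably closely related, which pulls the figure towards the lower end of the range.

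Much of this stands. The 5% level is an assumption, and the absence of a primary outcome can be asserted only for these two documents. A high correlation does lower the figure, and this is why the range extends to 9.4%. But prominence in a title is not a designation. If both title outcomes are taken as primary, no rule says whether one or both must succeed. Leaving the level unstated is part of the gap and does not answer it.

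Two stronger readings are tempting, and the documents support neither:

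- A reader might infer that the four outcomes rank equally and that any one of the 12 tests may be declared a success. The SAP is silent on ranking and on success. It does not grant that licence.
- A reader might pool all 12 tests and quote 1 − 0.95^12 = 46.0%. That mixes two hypotheses: no change over 12 weeks within an arm, and no difference between arms. The tests also cannot be independent, because the between-group tests reuse data from the within-group tests. Simulation that keeps this dependence gives 38.6% to 44.3% with uncorrelated outcomes and 20.4% to 24.3% at a correlation of 0.9. The range depends on whether the between-group test uses changes or post-intervention values (the latter with an assumed pre-post correlation of 0.5). Even these lower figures do not measure error in the comparison of arms.

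**Conclusion.** The point holds for the between-group comparison. With no primary outcome, significance level or multiplicity rule in either document, the four between-group tests carry about a 9% to 19% chance of at least one false positive, roughly 2 to 4 times the nominal level. The two title outcomes alone carry up to 9.75%. These figures assume two-sided 5% per test, no true difference on any outcome, and equal correlations between 0 and 0.9. The eight within-group tests should be kept apart from this family: they answer a different question and cannot support a treatment effect in a trial with two active arms.

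The timing limits the remedy. The SAP is in the past tense and reports what the normality tests showed, so a reader might think that naming a primary outcome or a testing order now would restore 5% control. It would not, because the choice would follow sight of the data.

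**What to change.** 1. Base conclusions on the between-group comparisons only. Estimate each as the post-intervention difference adjusted for the baseline value of the same outcome, with a 95% confidence interval. This also settles which values are compared. No new data are needed, since the planned before-after tests already require both values.
2. If a primary outcome was fixed before the data were seen, state it, cite the dated record and test it at two-sided 5%.
3. If none was fixed, either apply Holm or Bonferroni across the four between-group tests (Bonferroni 0.0125 each; Holm starts at 0.0125 for the smallest p-value) or label all four exploratory. Report all four in either case.
4. Report the eight within-group results as changes with 95% confidence intervals, without efficacy claims.
5. Label any primary outcome chosen now as post hoc.

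The cost is a small re-analysis, because baseline adjustment replaces the independent t-test, together with revised text. Fewer results can then be claimed as confirmatory.

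### For IPAQ and body fat percentage the SAP finds non-normality and uses a rank test within arms, but compares the arms only by an unexplained independent t-test on an unstated quantity, with no named use of the baseline

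*SAP*

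**What the plan says.** The SAP treats four outcomes in parallel paragraphs.

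- BMI and serum testosterone are declared normal: "the data was normally distributed so paired T-test was performed for within group analysis". The arms are then compared by an independent t-test.
- Body fat percentage is declared non-normal: "For Body fat percentage: Shapiro-Wilk test was used to determine the normality of data. The data was not normally distributed". The consequence drawn is a signed-rank test within each arm. The arms are again compared by an independent t-test.
- IPAQ follows the body fat sequence: "For IPAQ: Shapiro-Wilk test was used to determine the normality of data. The data was not normally distributed", then signed-rank within arms and an independent t-test between them.

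The body fat and IPAQ paragraphs share the same words at the decisive point: "The data was not normally distributed so, Wilcoxon sign rank test was performed for within group analysis. Independent T-test was performed for the comparison".

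The protocol's Study Protocol section shows that both non-normal outcomes have a baseline value ("skinfold measurement for body fat had been taken by the chief examiner and International physical activity questionnaire for physical activity measurement") and a final value ("At the end of the last intervention session, all outcome measures were reassessed").

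The SAP does not say which data went into Shapiro-Wilk (baseline, post or change; pooled or by arm). It does not say which quantity the between-arm t-test compared. It mentions no transformation, baseline adjustment or sensitivity analysis.

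**The concern.** The normality result changes the within-arm test and never the between-arm test. For IPAQ and body fat percentage the SAP treats non-normality as a reason to leave the t-test for the paired comparison, then uses a t-test for the comparison of arms without comment. That comparison is the one that answers the question of HIIT against strength training, and physical activity is named in the study title.

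Three things are at stake.

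- **Definition.** A reader cannot tell whether the t-test compared final values or changes, so cannot reproduce it or say whether the baseline was used. This needs no assumption about the data.
- **Power.** If the compared quantity is strongly right-skewed, a few extreme values dominate the mean difference, and the t-test may miss a difference that a rank test would find.
- **Efficiency.** A baseline was collected, and no use of it between arms is named.

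**Working it through.** **1. Text.** Set side by side, the four paragraphs read:

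| Outcome | Normality | Within arm | Between arms |
|---|---|---|---|
| BMI | normal | paired t | independent t |
| Serum testosterone | normal | paired t | independent t |
| Body fat % | not normal | signed-rank | independent t |
| IPAQ | not normal | signed-rank | independent t |

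The last column never changes. No general rule for choosing the between-arm test is stated.

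**2. Inputs for size.** The documents give no sample size, SD, skew, effect size or IPAQ scoring, so the plan has no figure to reproduce. The illustration is a simulation in which every input is assumed: two equal arms of 20, log-normal baseline and post values, log-scale correlation 0.5, two-sided 5%, and 20,000 replicates per cell for the 0.8-shift tables. Strong skew means log-SD 0.8 to 1.2; mild skew means 0.15 to 0.3.

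**3. Strong skew, shift 0.8 log-SD. Power (%):**

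| log-SD | t, post | Mann-Whitney, post | t, change | ANCOVA | Quade |
|---|---|---|---|---|---|
| 0.8 | 57.1 | 67.2 | 60.9 | 64.8 | 77.4 |
| 1.0 | 50.6 | 66.9 | 53.7 | 57.5 | 76.9 |
| 1.2 | 43.8 | 66.7 | 45.2 | 49.4 | 77.0 |

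Mann-Whitney minus t on post values: 67.2 − 57.1 = 10.1; 66.9 − 50.6 = 16.3; 66.7 − 43.8 = 22.9 points. Quade minus Mann-Whitney on post values: 10.2, 10.0 and 10.3 points.

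**4. Smaller effect.** A shift of 0.8 log-SD is a ratio of exp(0.8 × 0.8) = 1.9 to exp(0.8 × 1.2) = 2.6 between two supervised exercise arms, which is large. At 0.3 log-SD, t against Mann-Whitney on post values is 12.1 v 14.5, 10.1 v 13.9 and 8.6 v 14.3%. The gaps are 2.4, 3.8 and 5.7 points, and both tests are badly underpowered.

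**5. A different model.** Take a strongly skewed baseline (log-SD 0.8 to 1.2) and a normally distributed change (SD 0.7 times the baseline SD, shift 0.8 change-SD, 20 per arm). Power is about 69–70% for the t-test on change, 66–68% for Mann-Whitney on change and 58–59% for Quade. Here Quade loses about 10 points to a test the trial may already have run.

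**6. Mild skew, shift 0.8 log-SD. Power (%):**

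| log-SD | t, post | t, change | ANCOVA |
|---|---|---|---|
| 0.15 | 68.5 | 70.7 | 78.8 |
| 0.2 | 68.5 | 71.6 | 79.4 |
| 0.3 | 67.6 | 70.8 | 77.6 |

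Over mild-skew cells with 15 to 40 per arm, the t-test on post values is 0.2 to 4.0 points ahead of Mann-Whitney, so ranking gains nothing. The gain comes from the baseline: ANCOVA is 6.8 to 8.1 points above the t-test on change (77.6 − 70.8; 78.8 − 70.7) and 10.0 to 10.9 above it on post values (77.6 − 67.6; 79.4 − 68.5). In step 3 ANCOVA also beats both t-tests, though it does not recover the loss from not ranking.

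**7. False positives.** With no true difference, over 15 to 40 per arm and all skews, the t-test rejects in 3.1–5.3%, Quade in 4.5–5.4% and ANCOVA in 3.2–5.2%. With unequal arms (10:30, 15:30, 12:20) and log-SD 1.0 and 1.2, the t-test rejects in 3.5–4.9%.

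**The case against.** The strongest reply is that no error is shown in the test actually run. The data that failed Shapiro-Wilk need not be the quantity the t-test compared. If raw scores were tested for normality and changes were compared, the changes might be close to normal, and a t-test on change would use the baseline without the SAP saying so. This stands. It would weaken if Shapiro-Wilk was applied to the within-person changes, which is the natural check before a paired test, but the SAP does not say.

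Second, the large gaps come from a log-normal model with a multiplicative shift, which favours ranks, and from a large effect. This also stands: steps 4 and 5 of the working show the gap shrinking and the ranking of methods reversing. If IPAQ was analysed in a few categories, the strong-skew figures do not apply to it.

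Third, the missing baseline is not specific to these two outcomes, because BMI and serum testosterone get the same between-arm sentence. That is correct, and the fix covers them.

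Fourth, the SAP is written with the normality results known, so any new analysis is post hoc. This is a reason to label it and to keep the t-test, not to leave the comparison undefined.

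None of this supplies the missing reason, the missing definition or a named use of the baseline.

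**Conclusion.** The concern holds as an unexplained inconsistency and an undefined between-arm comparison. **Should fix** for IPAQ, because physical activity is a titular outcome; **minor** for body fat percentage. Confidence is high for the text and moderate for the size.

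Under the assumed strong skew at 20 per arm, the t-test on post values gives up about 10 to 23 points of power to Mann-Whitney at a 0.8 log-SD shift and 2 to 6 points at 0.3.

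A reader might infer four stronger things that the documents do not support:

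- **That the t-test is invalid or gives too many false positives.** Its simulated error rate is at or below about 5%.
- **That the SAP broke its own rule.** It states no rule for the between-arm test.
- **That IPAQ is known to be more skewed than body fat percentage.** The wording for both is the same and no distribution is given. Strong skew for one and mild for the other is an assumption.
- **That Quade should replace the t-test for IPAQ.** It gains about 10 points over Mann-Whitney on post values in one model and loses about 10 to the t-test on change in another.

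**What to change.** 1. State which data Shapiro-Wilk tested (baseline, post or change; pooled or by arm) and whether the independent t-test compared post-intervention values or change. Keep reporting that test as performed.
2. For body fat percentage, add: *Post-intervention values were compared between arms by ANCOVA with the baseline value as covariate; the adjusted mean difference is given with its 95% CI.* Do the same for serum testosterone, and for BMI where a baseline value exists. The protocol's baseline list omits BMI, although the SAP's paired test implies one.
3. For IPAQ, add one rank comparison that uses the baseline, as a labelled sensitivity analysis beside the t-test. It can be Quade rank ANCOVA, or Mann-Whitney on change with its matching Hodges-Lehmann difference and 95% CI. Name which one before running it. Give median (IQR) of post values and of change by arm.
4. Label items 2 and 3 as post hoc, chosen after the normality results were known.

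**Cost.** A few sentences and a short re-run on data already collected. The SAP names only one package ("the data was entered and analyzed in MedCalc software version 19.0.5"), so Quade may have to be built in steps or run elsewhere. The rank result may disagree with the t-test. Quade gives no mean difference and can be less powerful than a t-test on change. The two rank options can also disagree with each other: under the strong-skew model at 20 per arm they differ on significance in about 23%, 17–19% and 9–10% of trials at correlation 0.3, 0.5 and 0.7. That is why one must be named first.
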